The analysis plan for each specific hypothesis is listed below. In addition to hypothesis testing to analyze effects of the intervention on sleep, PAP adherence, depressive symptoms and quality of life, we will develop models showing which covariates predict the values of each of the outcome measures. Prior to hypothesis testing, data will be cleaned, possible outliers identified, and data distributions evaluated for assumptions of analysis (e.g. normality, homogeneity of variance). If necessary, normalized rank transformations as described in Bonate²⁴ will be performed and normalized rank scores will be submitted to analysis.

Hypothesis 1: Compared to control participants, participants randomized to the intervention will have improved nighttime sleep (i.e., higher sleep efficiency, better self-reported sleep) and better PAP adherence (measured objectively) at 3-months follow-up.

This hypothesis tests for differences between the intervention and control groups in our primary outcome measures of nighttime sleep and PAP adherence, between baseline assessment and 3-months follow-up, which is our primary time endpoint. Subjective measures of sleep outcomes will include sleep diary (sleep onset latency, wake after sleep onset [WASO], and sleep efficiency) and sleep quality (PSQI). The objective measure of sleep outcome will be actigraphy (sleep efficiency), and the objective measure of PAP adherence will be downloaded from the PAP smart card (percent of nights with PAP use \geq 4 hours, and mean hours of PAP use per night). All outcomes will be assessed using intention to treat analyses. A 2 X 2 (time X group; where time = baseline or 3-month assessment; and group = intervention or control) analysis of covariance analysis will be used with Bonferroni-corrected post-hoc comparisons to investigate differences between the groups in terms of treatment effects in the sleep variables (where baseline and 3-month follow-up data will be available). For PAP adherence outcomes, there will be no “baseline” data (i.e., PAP adherence data isn’t available until the participant starts PAP therapy), so outcomes between groups will be compared with independent samples t-tests and Chi-square test for difference in proportions.

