We expect that the group by time analysis of covariance for the sleep variables will show a difference between groups, and post-hoc analyses will show increased nighttime sleep efficiency and improved self-reported sleep (indicated by lower PSQI scores) in the intervention group compared to the control group. Following review of graphical representation of our longitudinal results (on main outcome measures), we will use repeated measures ANCOVA models to test both linear and nonlinear (i.e., quadratic) differential changes over time. Post-hoc tests within each time point (using Tukey type 1 error control) will be conducted. We expect there will be no difference between intervention and control groups at baseline, but differences will be present at follow-up. Other participant characteristics will be considered as possible covariates to reduce bias in our estimate of treatment effects and to increase precision. The major covariates that we expect to consider are age, cognition (estimated by MMSE) and comorbidity (estimated by CIRS-G). Other covariates we will consider include specific diagnoses and medications that may interfere with sleep, and measures of the intervention process (DBAS-16 scores, Self-efficacy, Knowledge and Decisional Balance Index subscales).

Sample size calculations were performed for each of the main outcome variables using reported effect sizes and/or calculated effect sizes from reported sample means and standard deviations reported in the literature in prior studies of CBT-I for insomnia and behavioral PAP adherence interventions in outpatient adults (see Table 5). Prior literature indicates that CBT-I is an extremely potent intervention for insomnia, and the studies typically have large effect sizes and small samples. Some caution is warranted, however, since efficacy studies usually employ tightly controlled ‘ideal’ treatment conditions, which also yield larger effect sizes

than effectiveness studies with more ‘real world’ conditions. Regardless of these issues, even the most conservative estimates of effect size from the literature suggest we will have an adequate sample size to test our sleep outcomes. A recent meta-analysis of trials of PAP adherence interventions published as a Cochrane review was used in estimating sample size for the PAP adherence component of our intervention.^{Error! Bookmark not defined.} this analysis suggests we will have an adequate sample size to test our PAP adherence outcomes.

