Sleep diary	Germain ^{Error! Bookmark not defined.}	.67	19	22
Sleep efficiency				
Sleep diary	Espie ^{Error! Bookmark not defined.}	.68	13	15
	Germain ^{Error! Bookmark not defined.}	.64	16	19
Actigraphy	Edinger ^{Error! Bookmark not defined.}	.60	27	32
Sleep onset latency				
Sleep diary	Espie ^{Error! Bookmark not defined.}	.58	20	23
	Germain ^{Error! Bookmark not defined.}	.80	10	12
Sleep quality				
PSQI, similar scales	Edinger ^{Error! Bookmark not defined.}	.58	20	23
	Germain ^{Error! Bookmark not defined.}	1.37	10	12
PAP adherence				
	Cochrane Review ^{Error! Bookmark not defined.}	.59	47	54
	Olsen ^{Error! Bookmark not}	.55	54	62

	defined.			
	Richards ^{Error! Bookmark not defined.}	1.12	14	16
Depression				
Hamilton Depression Scale	Germain ^{Error! Bookmark not defined.}	.67	14	16
Quality of life				
SF-36	Buysse ^{Error! Bookmark not defined.}	.57	50	58

Hypothesis 2: Compared to control participants, participants randomized to the intervention will report fewer depressive symptoms and better health-related quality of life at 3-months follow-up.

This hypothesis tests for differences between the intervention and control groups in depressive symptoms (using the PHQ-9) and health-related quality of life (using the SF-12v2) between baseline assessment and 3-months follow-up. All outcomes will be assessed using intention to treat analyses in an identical manner as described for Hypothesis 2. For sample size calculations, we used data from studies that used the same instrument as planned for the current proposal (if available) or from studies where similar measures were used, if results from the identical measure were not available (see Table 5).

Hypothesis 3: Compared to control participants, participants who receive the intervention will maintain improvements in sleep, PAP adherence, mood and quality of life at 6-months follow-up.

This hypothesis tests for differential change in outcomes between the intervention and control groups from baseline to follow-up assessment at 6 months, to test for maintenance in differences between intervention and control groups in the key sleep, PAP adherence, depressive symptoms and quality of life outcomes at 6 months follow-up. The statistical analyses used will be the same as described for Hypotheses 1 and 2.

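### The main sleep analysis is called analysis of covariance but is specified as a group-by-time test of change; adjusting the 3-month value for baseline and AHI stratum would be at least as efficient in large samples, at almost no cost

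*Combined protocol and SAP*

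**What the plan says.** Under Analysis Plan and Hypotheses, Hypothesis 1, the sleep variables are to be tested by "A 2 X 2 (time X group; where time = baseline or 3-month assessment; and group = intervention or control) analysis of covariance", followed by group comparisons "with Bonferroni-corrected post-hoc comparisons to investigate differences between the groups in terms of treatment effects in the sleep variables". The expected result is worded the same way: "We expect that the group by time analysis of covariance for the sleep variables will show a difference between groups".

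On covariates, the plan states: "The major covariates that we expect to consider are age, cognition (estimated by MMSE) and comorbidity (estimated by CIRS-G". Diagnoses, medications and process measures may follow. The outcome's own baseline value is not listed.

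For the longitudinal model, "Post-hoc tests within each time point (using Tukey type 1 error control) will be conducted", and the plan adds: "We expect there will be no difference between intervention and control groups at baseline, but differences will be present at follow-up". Baseline is therefore handled as an outcome there too.

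Hypothesis 3 describes its purpose in change terms: "This hypothesis tests for differential change in outcomes between the intervention and control groups from baseline to follow-up assessment at 6 months". It then says: "The statistical analyses used will be the same as described for Hypotheses 1 and 2". Hypothesis 2 points to itself for its method. The belief and attitude scales under Hypothesis 4 use the Hypothesis 1 analysis.

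Randomization is stratified by AHI (below 30; 30 or above). In the analysis the stratum appears only in the block-by-group interaction test under Potential Shortcomings in the Proposed Analysis.

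**The concern.** The label and the specification describe different tests. Analysis of covariance in a pretest-posttest trial normally means regressing the follow-up value on group and baseline. A 2 X 2 model with baseline as a level of time, judged by its interaction, tests the difference in mean change. Adding age, MMSE or CIRS-G makes it a covariate-adjusted change comparison, but still a change comparison.

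Both tests are unbiased under randomization, but they can give different p-values at the primary time endpoint. The change test gives up precision unless k equals r. Table 5 also defines its effect size as a difference at follow-up divided by the SD, which fits a comparison of follow-up values better than a comparison of change. The choice carries through to depression and quality of life (Hypothesis 2), to 6 months (Hypothesis 3) and to the Hypothesis 4 scales.

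**Working it through.** **Inputs from the documents.** Two-sided .05 and 80% power; 60 per group randomized; 51 per group expected at 6 months after 15% loss. The 3-month number lies between 51 and 60. d=.58 is the smallest sleep effect in Table 5, and d=.57 is the quality-of-life row.

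**Assumed, because the documents give neither.** r from .3 to .8 and k from .7 to 1.2.

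**The plan's own figures.** A two-sample t-test for 80% power needs 50 per group at d=.57 (Table 5: 50) and 10 at d=1.37 (Table 5: 10), so these rows reproduce. At d=.58 it needs 48, where Table 5 has 20. If the non-matching rows are read as change-score calculations with equal SDs, the r that each needs is: WASO .74; diary sleep efficiency .82 and .81; actigraphy .70; sleep onset latency .80 and .82; PSQI (d=.58) .80; depression .82. Seven of the eight sleep rows would then imply r of .70 to .82. This is only an inference, since d is defined at follow-up.

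**Variances, in units of the follow-up variance.**
- Change score: 1 + k² − 2rk
- Follow-up adjusted for baseline: 1 − r²
- Difference: (1 + k² − 2rk) − (1 − r²) = (k − r)², which is never negative and is zero only at k = r.

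Example with k=1, r=.3: 1.40 − .91 = .49 = (1 − .3)².

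**Power (noncentral t).** The standardized effect for change is d/√(1+k²−2rk), with 2n−2 df. For the adjusted test it is d/√[(1−r²)(1+1/(2n−4))], with 2n−4 df, so the cost of estimating the baseline slope is included. The noncentrality is the effect times √(n/2). At r=.3, k=1, n=51:
- change: .58/√1.40 = .490, times √25.5 = 2.48, power 68.8%
- adjusted: .58/√(.91 × 1.0102) = .605, times √25.5 = 3.05, power 85.6%

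d=.58, k=1, change v adjusted (%):

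| r | 51 per group | 60 per group |
|---|---|---|
| .3 | 68.8 v 85.6 | 75.9 v 90.8 |
| .5 | 82.7 v 91.5 | 88.3 v 95.2 |
| .6 | 90.0 v 95.0 | 94.1 v 97.5 |
| .7 | 96.3 v 98.1 | 98.2 v 99.3 |
| .8 | 99.6 v 99.8 | 99.9 v 99.9 |

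A simulation of 40,000 trials per setting, with baseline and stratum in the adjusted model, agrees. At 51 per group it gives 68.9 v 85.7% (r=.3), 82.6 v 91.5% (r=.5) and 96.1 v 98.0% (r=.7).

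**Ignoring baseline.** A plain follow-up t-test has 82.7% power at 51 per group. With equal SDs the change test is therefore weaker than discarding baseline whenever r is below .5.

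**Unequal SDs** (51 per group, r=.3/.5/.7). At k=1.2 the change test has 60/74/91%, and at k=.7 it has 80/90/98.2%. The adjusted test has 86/91.5/98.1% in both cases.

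**Quality of life** (d=.57, k=1). At r=.3: 67 v 84% (51) and 74 v 90% (60). At r=.5: 81 v 91% (51) and 87 v 94.5% (60). The change test reaches 80% only if r is at least about .48 (51) or .39 (60).

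**Worst case for adjustment** (r=0, d=.58, against a follow-up-only test). 82.7 v 81.9–82.3% (51) and 88.3 v 87.8–88.0% (60); the lower figures also charge a degree of freedom for the stratum.

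**The case against.** The planned test is valid, and the benefit of replacing it is not demonstrated. The large contrasts come from an assumed r of .3. On the one reading that takes r from the documents, the planned test already has at least 96% power at 51 per group and gains 0–2 points. The figures also use the smallest sleep effect. At d=.67, equal SDs and 51 per group, the change test has 81% power even at r=.3, and at d=.80 it has 92%. The figures at 60 per group apply the full effect, although the plan assumes that dropouts do not change on average. The sponsor may also have meant ordinary baseline-adjusted analysis, since the label says so and the covariate list is not closed.

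Most of this stands as a limit on size. For the sleep outcomes the gain may be small, and the figures at 60 are optimistic for both tests. The quality-of-life row is different: it matches a plain two-sample test and gives no support for a high r. The charitable reading does not fit a time factor with baseline as a level, a group-by-time result, or a test of differential change. If it was the intention, the text still needs the same edit. In finite samples the change test can lead when k is close to r, but only by a fraction of a point (98.2 v 98.1% at k=r=.7).

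**Conclusion.** The point holds as one of efficiency and specification, not bias. The main sleep analysis is a change-score test under another name and, in large samples, is never more efficient than adjusting the follow-up value for baseline. With d=.58, equal SDs and 51 per group, the loss is about 17 points of power at r=.3, 9 at r=.5, 2 at r=.7 and almost none at r=.8. It is larger if the baseline SD exceeds the follow-up SD and nearly vanishes at k=.7 with r=.5 or more. Since r and the SDs are not given, the actual loss cannot be stated. The shortfall below 80% is most plausible for quality of life. No separate power gain is claimed for the AHI stratum; it belongs in the model because randomization used it. The change should be made because the possible gain far exceeds the possible cost.

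**What to change.** For each sleep, depression and quality-of-life outcome, define the primary test as the group coefficient in:

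3-month value = group + baseline value of the same outcome + AHI randomization stratum (below 30; 30 or above) + any prespecified baseline covariates.

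- Use the same model at 6 months and for the belief and attitude scales.
- It replaces both the 2 X 2 group-by-time test and the post-hoc group comparison after it, because the coefficient is itself the between-group difference at follow-up.
- Run it under both planned missing-data analyses (all available data, then after EM estimation).
- If the rank transformation is used, state how it applies to the baseline value as well as to follow-up.
- In the longitudinal model, drop the between-group post-hoc test at baseline.
- Point Hypothesis 2 to the Hypothesis 1 model.

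PAP adherence has no baseline and is unaffected. Multiplicity across outcomes is a separate matter that this does not address.

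The cost is SAP wording and two degrees of freedom. Even if baseline carried no information, the loss against a follow-up-only test would be under one percentage point.

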This 3.5 year project will be a randomized controlled trial testing a combined, integrated behavioral approach to management in older Veterans (aged ≥ 50 years) who are diagnosed with OSA, are prescribed PAP therapy, and also meet diagnostic criteria for insomnia. This novel intervention will combine essential elements of a CBT-I intervention (for insomnia) plus a behavioral intervention to improve PAP adherence. The combined, integrated intervention will be provided using allied health personnel compared to an active control condition (consisting of a general sleep and PAP education program) among older Veterans (N=120 total participants, 60 per group). Structured outcome assessments will be collected at baseline, post-treatment (i.e., after completion of the intervention or control condition), and at 3- and 6-months follow-up. A brief telephone interview will be conducted at 12-month follow-up. Outcomes assessed will include subjective (i.e., questionnaire, sleep diaries) and objective (i.e., wrist actigraphy) measures of sleep, objective measures of PAP adherence (downloaded from PAP equipment), mood and other measures of health-related quality of life. Data will also be collected at post-treatment, and at 3- and 6-months follow-up to assess beliefs and attitudes about sleep and OSA. Adherence with key aspects of the intervention will be collected in intervention participants during the treatment phase, and intervention participants will be invited to participate in focus groups after completing their 6-month follow-up to identify factors that act as facilitators or barriers to participation and adherence with the intervention.

Setting

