
In the second step of recruitment, consented Veterans who have completed baseline testing, are diagnosed with OSA (based on sleep clinic physicians interpretation of sleep study results) and are prescribed PAP therapy (by sleep clinic clinicians) will be reminded of study procedures, and invited to participate in the randomized controlled trial. Inclusion criteria will include: 1) age \geq 50 years, 2) meeting ICSD2 diagnostic criteria for insomnia, and 3) diagnosis of OSA with an AHI \geq 15 and prescription of PAP therapy. Exclusion criteria for randomization will include the following: 1) refusal to schedule an appointment to begin PAP therapy, 2) a Mini-mental State Examination (MMSE) score < 24 (used to screen for significant cognitive impairment), and 3) a history of mania (which is a contraindication for the sleep restriction component of CBT-I), major psychopathology (e.g., psychosis) or a psychiatric hospitalization within the prior two years.

- Randomization

Participants will be randomized to the intervention or control group using a randomized block design based on results from the OSA testing, to increase the likelihood of comparable severity of OSA in both groups. Specifically, individuals will be categorized based on AHI < 30 or AHI \geq 30. Consented participants will be randomized as a block within each category (similar to block randomization techniques we have used in prior research). Available randomization software (e.g., Random Allocation Software, Paradigm) which allows for block randomized sequences for parallel group randomized trials will be used to assign participants to the intervention or control group, using random allocation concealment. Participants and research staff (except intervention staff) will be blinded to group assignment, and additional techniques (e.g., follow-up assessment in some consented, non-randomized participants) will be used to prevent unmasking. It may be difficult to keep assessment research staff blinded to group assignment if participants inadvertently describe their assignment, but all assessment staff will also be blinded to study research questions.

Dependent and Independent Variables (Measurement Techniques)

A summary of all measurement techniques is shown in Table 1.

Baseline Assessment

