- PAP adherence. In addition,
- PAP equipment will be provided by the VA GLAHS Sleep clinics to all intervention and control participants per usual care established clinical protocols. The VA GLAHS Sleep clinics nearly exclusively use Respiromics™ devices (Respiromics, Inc., Murrysville, PA). The PAP devices are routinely dispensed with heated humidification to minimize upper airway dryness, which may affect adherence. The same clinical staff (i.e., sleep technicians) will provide PAP equipment and usual setup instructions for both intervention and control participants; these clinical staff will be blinded to group assignment. All PAP devices have an internal secure device (SD) memory card that stores PAP usage data and a modem that transmits daily usage to a web-based application (EncoreAnywhere) maintained on a secure server by Philips Respiromics, Inc. The data on the server are linked only to the serial number of the PAP modem and do not include any personal identifiers. Authorized research staff will retrieve data from the server using an assigned password. Philips Respiromics, Inc. will have no access to the key that links PAP modem serial number to subject identification code or name. For participants who are unable to use the modem because they live outside the modem serve area, research staff will download the SD card (easily performed with an inexpensive reader device) at the time of the follow-up assessments. Data will be obtained after the first week of PAP therapy, at the post-treatment assessment, and at 3- and 6- and 12-months follow-up. Our primary dependent measure of PAP adherence will be the percentage of nights that the PAP equipment was used for \geq 4 hours per night. In addition, we will define "adequate" PAP adherence as PAP usage of \geq 4 hours per night for 70% of days, and we will also record the mean hours of PAP use per night.²³ PAP machines have the capability to sense when the mask is on the patient's face, so we will be able to assess the hours per night of use at the effective PAP pressure (i.e., mask on at an effective pressure). Adherence data is automatically stored continuously in PAP equipment, and available by day. We plan to summarize data over the prior 7 days (at all data collection time-points) and/or the prior 30 days where appropriate (i.e., at 3-, 6-, and 12-months follow-up).

Treatment groups

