Participants will be randomized to one of two groups: 1) intervention group, who will receive an integrated, manual-based individual CBT-I plus PAP adherence behavioral self-management program, or 2) control group, who will receive an attention control condition (general sleep and OSA education). All participants will be prescribed PAP therapy (through the sleep clinic), and will receive their PAP device through the sleep clinic, as described above. The intervention and control conditions will be provided by research allied health personnel (i.e., not psychologists). The active intervention was designed to have a high enough intensity/potency for efficacy, while avoiding as much as possible the risks of excessive participant burden and excessive costs of implementation into routine care if successful. In addition, the intervention is structured and manual-based (i.e., using a concise intervention manual) in order to be highly translatable to routine care. The intervention and control programs will begin after baseline assessment and randomization, and the intervention or control conditions will begin approximately 2 weeks prior to initiation of PAP therapy. If there is a delay in receipt of PAP equipment, participants will receive a weekly phone call from intervention/control staff to monitor progress and provide reinforcement (of information learned in sessions 1 and 2 in the intervention group, and to encourage continued participation in the control group). If the PAP equipment is received prior to completion of sessions 1 and 2, the intervention/control condition will progress as scheduled below over a 6 week period.

Intervention condition

The intervention provides an integrated behavioral approach to OSA and insomnia, which combines a CBT-I treatment for insomnia with an OSA and PAP self-management program. The aspects of each intervention are integrated seamlessly into one intervention program, provided in individual (i.e., one-to-one) sessions with master's level allied health personnel (e.g., health educator) (see Appendix 3 for example of session material). The first two sessions will be timed to occur prior to the patient receiving their PAP equipment; sessions 3 – 5 will occur after the participant receives their PAP device, with session 3 timed to

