For the proposed study, we calculated sample size based on the outcome at post-treatment, and either the reported effect size (d) or d calculated from the reported means and SDs. The table below lists sample size needs for the entire duration of the study (i.e., 6 months). Based on an expected 15% loss by six months, the 5th column in the table below projects the sample size needed for each of 2 groups at randomization to maintain sufficient sample size at 6 months to test the selected outcomes.

Table 5 lists expected effect size, shown as the variable “d” (difference between intervention and control groups at follow-up divided by standard deviation). For many outcomes, we list several expected effect sizes from the literature; references for these effect sizes are listed in the second column. The effect size estimates take into account expected change in controls over time, since we expect controls will change, but not as much as the intervention group. The sample size needed at randomization to detect effect size d is shown (column 4), followed by the number of enrolled participants needed for the 6-month analyses (column 5), taking into account expected dropout by this time point. Based on these calculations, 120 randomized participants (60 per group) will be adequate for analyses at both 3 and 6 months. In addition to these main analyses, we will perform follow-up subgroup analysis to identify two or three variables which identify participants who have the greatest positive response to the intervention. Testing for subgroups with better or worse response results in such a small sample that overfitting is a potential problem; this risk is discussed below.

For example, in Table 5 the third row (WASO by sleep diary) shows that to have the needed sample size (N=19 per group) completing the study (i.e., with follow-up assessment data) to test for an effect (based on an expected 15% participant loss by 6 months), we need to enroll 22 participants per group (column 5) at baseline to have 19 participants per group remaining at 6 months follow-up. For all variables listed, we expect an adequate sample size to test our hypotheses. For all sample size calculations, the dropouts are assumed not to change on average. All testing assumes a two-sided .05 significance level with 80% power.

Table 5: Sample size calculations

Outcome	Reference	Reported (or calculated) effect size d	Enroll per group for d: post-test	Enroll per group for d at 6 months
WASO				

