There are statistical problems we may encounter in analyses, including the statistical handling of participant dropout, possible differential treatment effects across randomization blocks, and the risk of overfitting the data. To deal with dropouts, we will use standard "intention to treat" analysis. The main independent variable will be whether a participant is in the intervention or control group, rather than whether the participant actually receives the intervention. If the participant rejects the intervention at some point after randomization, but allows us to collect follow-up data, we will use standard "intention to treat" analysis. If the participant stops providing data, we will do analyses using all available data, and then repeat analyses after estimating missing data using an EM (expectation-maximization) algorithm, which is less subject to bias than other methods such as carrying forward the last available value; results from both analyses will be reported. It is important to address dropouts, since those who complete the study may be more compliant or healthier than those who drop out. To understand how "completers" may differ from "dropouts", we will compare their baseline characteristics. Dropout rates and characteristics of dropouts will also be compared between groups.

To address the risk of a differential effect of the intervention between randomization blocks, we will test for a block by group interaction. If one is present (suggesting the treatment is more or less effective for one stratification group over another), the results cannot be pooled, which impacts statistical power. However, we anticipate overall treatment effect will overshadow any differential effects across stratification blocks.

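### The plan promises intention to treat but gives no PAP adherence value for randomised participants who never receive or start PAP, or who have returned the device

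*Combined protocol and SAP*

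**What the plan says.** All references are to the combined protocol and SAP.

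- **Study Population, second recruitment step.** Randomisation requires an OSA diagnosis and a PAP prescription. The only PAP-related exclusion is "refusal to schedule an appointment to begin PAP therapy". Having or using a device is not required.
- **Treatment groups.** Both programmes start after randomisation, and "the intervention or control conditions will begin approximately 2 weeks prior to initiation of PAP therapy". Late equipment is foreseen and met with weekly calls; no analysis rule is attached.
- **PAP adherence (Sleep Assessment Monitoring).** "Our primary dependent measure of PAP adherence will be the percentage of nights that the PAP equipment was used for" at least 4 hours. Use is taken from the memory card or modem and summarised over the previous 7 days and/or, at the later visits, 30 days.
- **Hypothesis 1.** All outcomes are to be analysed by intention to treat. PAP data are not "available until the participant starts PAP therapy), so outcomes between groups will be compared with independent samples t-tests", with a chi-square test for proportions.
- **Potential Shortcomings in the Proposed Analysis.** Intention to treat is defined by assigned group. "If the participant stops providing data, we will do analyses using all available data, and then repeat analyses after estimating missing data" by an EM algorithm, and both results are reported.
- **Three-month follow-up assessment.** The main time point is counted from the baseline assessment, not from the start of PAP.

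No section says what adherence value a randomised participant receives if there is no device to read.

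**The concern.** Take a Veteran who books the set-up appointment, is randomised, attends sessions 1 and 2, and then never collects a device. There is nothing to download. Yet the person's PAP use is not unknown: it is 0% of nights and 0 hours. A Veteran who has handed the device back before the assessment window is in the same position for that window.

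Starting PAP happens after randomisation and may depend on arm. Table 2 shows that the first two intervention sessions cover OSA, PAP therapy, and the equipment and its set-up. Table 3 shows general sleep, OSA and health education in the control sessions of the same weeks. If never-starters are left out, or filled in from users, the PAP comparison describes people who started and not everyone randomised. Part of any benefit or harm, namely the effect on starting, disappears from a primary outcome. Two analysts could both follow this plan and report different PAP results.

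**Working it through.** **1. The plan's own figure.** Table 5 sizes PAP adherence on a standardised effect d, defined as the "difference between intervention and control groups at follow-up divided by standard deviation". "All testing assumes a two-sided .05 significance level with 80% power". The normal approximation is n per group = 2 × (1.960 + 0.842)² / d².

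| d | Normal | t-based | Table 5, post-test | Stated n × 1.15 | Table 5, 6 months |
|---|---|---|---|---|---|
| 0.59 | 46 | 47 | 47 | 54.05 | 54 |
| 0.55 | 52 | 53 | 54 | 62.1 | 62 |
| 1.12 | 13 | 14 | 14 | 16.1 | 16 |

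The stated sizes reproduce to within 2 per group. The calculation allows 15% loss by 6 months and makes no separate allowance for never starting. It also assumes that dropouts do not change on average, but PAP adherence has no baseline, so that assumption supplies no value here.

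**2. What the written rules yield for someone with no download.** Available-data analysis omits the person. EM assigns a value estimated from those with data. If the EM model uses arm only (the plan does not specify the model), that value is the mean of starters in the same arm, and the estimated difference equals the starters' difference. The two reported analyses would then agree with each other, and both would describe starters.

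**3. Size, by assumption.** The documents give no never-start rate and no mean or SD for PAP use. Assume starters reach 4 hours on 60% (intervention) and 50% (control) of nights, a difference of 10 points. With never-starters at zero, the mean over all randomised = (1 − never-start rate) × mean in starters.

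| Never start, intervention/control | Of 60 per arm | All-randomised difference |
|---|---|---|
| 5% / 15% | 3 / 9 | 0.95 × 60 − 0.85 × 50 = 14.5 |
| 10% / 10% | 6 / 6 | 0.90 × 60 − 0.90 × 50 = 9.0 |
| 15% / 5% | 9 / 3 | 0.85 × 60 − 0.95 × 50 = 3.5 |

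If starters average 55% in both arms and 5%/15% never start, the all-randomised difference is 0.95 × 55 − 0.85 × 55 = 5.5 points, where a starters-only comparison shows 0.

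Break-even: (1 − p_I) × 60 − (1 − p_C) × 50 = 10 gives p_C = 1.2 × p_I. Under these means, the starters-only figure is too small only if the control never-start rate exceeds 1.2 times the intervention rate. Otherwise it is equal or too large.

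**4. Second set of assumptions, tied to Table 5.** Control starters at 50%, SD 35, d = 0.59 among starters, so a starters' difference of 0.59 × 35 = 20.7 points. The all-randomised difference is 24.6, 18.6 or 12.6 points for 5%/15%, 10%/10% and 15%/5%. The pattern is the same.

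**5. What scoring zero does to power.** The plan has "N=120 total participants, 60 per group". Under the step 4 assumptions, with equal never-start rates and all 60 per arm analysed:

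| Never start, both arms | d, all randomised | Power | n per group for 80% |
|---|---|---|---|
| 0% | 0.59 | 89% | 47 |
| 5% | 0.54 | 83% | 56 |
| 10% | 0.49 | 76% | 67 |
| 15% | 0.45 | 69% | 79 |
| 20% | 0.42 | 62% | 92 |

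At 10% in both arms, the starters-only comparison (54 per arm) has 86% power against 76%. It gains this by answering a different question.

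**The case against.** The strongest reply is that the plan never says never-starters are excluded. A reader might infer that from Hypothesis 1, but the sentence there only explains why PAP has no baseline and so why a t-test replaces the time-by-group analysis. The available-data and EM rule is worded for participants who stop providing data, and a never-starter may still complete questionnaires and actigraphy. Scoring known non-use as zero is compatible with the intention-to-treat promise. All of this stands. It does not close the gap: intention to treat is defined by assigned group, which says who is compared and not what value they carry. If the missing-data rule does not reach the never-starter, no rule does.

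A reader might also extend the problem to every non-user. The documents do not support that. The device stores use by day, so one that was issued and never used may already show zero nights. The group is narrowed further by the exclusion for refusing to schedule, by the statement that the clinics will provide equipment to all participants, and by the weekly calls. These steps reduce the number; they do not make it nil.

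Finally, the rates are assumed, and the 15%/5% case needs the intervention to hinder starting, which nothing in the documents suggests. One might conclude that any bias is conservative. That does not follow either: with equal rates the starters-only figure is already too large (10 against 9.0 points).

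**Conclusion.** The concern holds as a gap in the definition of a primary outcome. Intention to treat is promised, randomisation precedes the device, and the adherence value of a randomised participant with no device data is undefined. The only written rules for absent data would treat a known zero as missing. The gap is clearest for those never issued a device, and it also covers those who returned it before the window.

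Neither the size nor the direction of any bias can be read from the documents. The 14.5, 9.0 and 3.5 points against 10 are illustrations. They rest on assumed never-start rates and assumed means among starters, held fixed across scenarios. They show that a starters-only result can err either way, not that it will err by a given amount. The rule should be settled before PAP outcomes are analysed by arm.

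**What to change.** In the PAP adherence section, Hypothesis 1 and Potential Shortcomings, state the following:

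1. A randomised participant with confirmed non-use in the assessment window (PAP never started, or device returned) scores 0% of nights and 0 mean hours.
2. EM estimation is restricted to use that is truly unknown: failed download, withdrawal of consent, death, or loss to follow-up with unknown device status.
3. How nights are counted when equipment is still pending for supply reasons. This matters because the 3-month visit runs from baseline. Zero should not be applied automatically to everyone without a device, since that would mix supply delay with behaviour. Add a sensitivity analysis scoring those nights once as 0 and once as missing.
4. The number of non-starters is reported by arm, and the starters-only comparison is kept as supportive.

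The cost is a few sentences and a record, for each participant, of whether and when a device was issued, started or returned. No new assessment is needed. The downside is more zeros and ties, hence a more skewed outcome. The rank transformation already allowed in the analysis plan helps with skew but does not break ties at zero. The standardised effect may also shrink, with the loss of power shown above if never-start rates are similar in the two arms.
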